5 ANALYSIS SETS

5.1 Full analysis set

The full analysis set includes all of targeted tumors ablated from all patients who have undergone an ablation with the investigational device.

5.2 Safety population

The study population that will be included in the safety analysis consists of all patients who have undergone an ablation with the investigational device.

5.3 Technical performance population

The technical performance population set includes all targeted tumors ablated from all patients who have undergone an ablation with the investigational device and have an assessment of technical performance.

5.4 Patient demographics/other baseline characteristics

Demographic and other baseline data will be summarized descriptively for the full analysis set.

6 DESCRIPTIVE ANALYSIS

6.1 Screening failures

The reason of screening failures will be provided.

6.2 Demographic data

Descriptive statistics (mean, SD, median, Q₁, Q₃, minimum, maximum) of the following continuous variable will be shown:

- Age (it will be calculated on the date of informed consent)

The categorical variables to be described (n, %) are:

- Sex
- Race

6.3 Type of liver tumors

The categorical variable to be described (n, %) is:

- Type of liver tumors

6.4 Data related to liver tumors: Liver Metastases

If **Liver metastasis** was selected on Selection Visit the following analyses will be shown:

6.4.1 Primary tumor

Descriptive statistics (mean, SD, median, Q₁, Q₃, minimum, maximum) of the following continuous variable will be shown:

- Time from date of diagnosis to study inclusion: Calculated on the day of signature of informed consent (date of informed consent – date of diagnosis)

The categorical variables to be described (n, %) are:

- Disease stage at diagnosis
- Tumor location
- Surgery, if yes, technique used will be described per all surgeries undergone
- Has the patient received neoadjuvant/adjuvant therapy? if yes, the following variables will be described for all records registered:
 - Neoadjuvant/Adjuvant
 - Treatment (Chemotherapy, Targeted therapy, Radiotherapy)
 - In case of chemotherapy or Targeted therapy, type of treatment will be described

6.4.2 Metastatic disease

Descriptive statistics (mean, SD, median, Q₁, Q₃, minimum, maximum) of the following continuous variable will be shown:

- Time from date of diagnosis of metastatic disease to study inclusion: Calculated on the day of signature of informed consent (date of informed consent – date of diagnosis of metastatic disease)

The categorical variables to be described (n, %) are:

- Tumor disease presentation
- Disease stage
- Number of metastasis sites
- Metastasis location:
 - Liver-only metastases
 - Extra-hepatic disease (lung, brain, bone, other)

Descriptive statistics (mean, SD, median, Q₁, Q₃, minimum, maximum) of the following continuous variable will be shown:

- Number of liver tumor nodules

Descriptive statistics (mean, SD, median, Q₁, Q₃, minimum, maximum) of the following continuous variable will be shown for all records registered:

- Size of tumor nodules (maximum diameter)

The categorical variable to be described (n, %) is for all records registered:

- Location of tumor nodules: liver segment

The categorical variables to be described (n, %) are:

- Prior liver metastases ablation, if yes, the following variables will be described for all ablations registered:
 - Technique used (n,%)
 - Number of tumor nodules ablated (mean, SD, median, Q₁, Q₃, minimum, maximum):
 - Size for all records registered (mean, SD, median, Q₁, Q₃, minimum, maximum)
 - Location: liver segment for all records registered (n,%)
 - Ablation result (n,%)

- Prior liver metastases resection, if yes, the following variables will be described for all resections registered:
 - Technique used (n,%)
 - Number of metastases resected (mean, SD, median, Q₁, Q₃, minimum, maximum):
 - Location: liver segment (n,%)
 - Ablation result (n,%)
 - Complications after liver resection, if yes:
 - Intra-abdominal infection
 - Wound infection
 - Steatohepatitis
 - Sinusoidal dilatation
 - Other
- Neoadjuvant/adjuvant therapy, if yes, the following variables will be described for all records registered:
 - Neoadjuvant/Adjuvant (n,%)
 - Treatment (Chemotherapy, Targeted therapy, Radiotherapy) (n, %)
 - In case of chemotherapy or Targeted therapy, type of treatment will be described (n,%)
- Has the patient receive any treatment for metastatic disease?, if yes, the following variables will be described for all records registered:
 - Type of treatment (n, %)
 - Response (n,%)
 - Number of cycles administered (mean, SD, median, Q₁, Q₃, minimum, maximum)
- Number of lines of treatment for metastatic disease (mean, SD, median, Q₁, Q₃, minimum, maximum)

6.5 Data related to liver tumors: Hepatocellular carcinoma

If **Hepatocellular carcinoma** was selected on Selection Visit the following analyses will be shown:

Descriptive statistics (mean, SD, median, Q₁, Q₃, minimum, maximum) of the following continuous variable will be shown:

- Time from date of diagnosis to study inclusion: Calculated on the day of signature of informed consent (date of informed consent – date of diagnosis)

The categorical variables to be described (n, %) are:

- Disease stage
- Barcelona-Clinic Liver Cancer staging

Descriptive statistics (mean, SD, median, Q₁, Q₃, minimum, maximum) of the following continuous variable will be shown:

- Number of liver tumor nodules

Descriptive statistics (mean, SD, median, Q₁, Q₃, minimum, maximum) of the following continuous variable will be shown for all records registered:

- Size of tumor nodules (maximum diameter)

The categorical variable to be described (n, %) is for all records registered:

- Location of tumor nodules: liver segment

The categorical variables to be described (n, %) are:

- Surgery, if yes, technique used will be described per all surgeries undergone
- Prior liver metastases ablation, if yes, the following variables will be described for all ablations registered:
 - Technique used (n,%)
 - Number of tumor nodules ablated (mean, SD, median, Q₁, Q₃, minimum, maximum):
 - Size for all records registered (mean, SD, median, Q₁, Q₃, minimum, maximum)
 - Location: liver segment for all records registered (n,%)
 - Ablation result (n,%)
- Prior chemotherapy, if yes, the following variables will be described for all records registered:
 - Type of treatment (n, %)

- Number of cycles administered (mean, SD, median, Q₁, Q₃, minimum, maximum)
- Prior intra-arterial treatments, if yes, the following variables will be described for all records registered:
 - Type (n, %)

6.6 Medical history

The categorical variables to be described (n, %) are:

- Has the patient any previous or current relevant medical condition?
- Description
- Type
- For each type “Does it continue?” will be described
- For each type “The patient is treated for this medical condition” will be described

6.7 Physical examination

6.7.1 Anthropometric data

Descriptive statistics (mean, SD, median, Q₁, Q₃, minimum, maximum) of the following continuous variables will be shown:

- Height
- Weight
- BMI

6.7.2 Vital signs

Descriptive statistics (mean, SD, median, Q₁, Q₃, minimum, maximum) of the following continuous variables will be shown:

- Temperature
- DBP/SBP
- Cardiac frequency
- Respiratory frequency

6.7.3 Physical examination

The categorical variables to be described (n, %) are:

- Result
 - Clinically significant
 - Not clinically significant

6.7.4 ECOG

The categorical variable to be described (n, %) is:

- ECOG

6.7.5 Standard 12 Lead electrocardiogram

The categorical variables to be described (n, %) are:

- Result
 - Clinically significant
 - Not clinically significant

6.8 Laboratory test

Descriptive statistics (mean, SD, median, Q₁, Q₃, minimum, maximum) of the following continuous variables will be shown:

- Haemoglobin
- Erythrocytes
- Leucocytes
- Neutrophils
- Basophils
- Haematocrit
- Lymphocytes
- Monocytes
- Eosinophils
- Platelets
- AST
- ALT
- GGT
- Alkaline phosphatase
- Total bilirubin
- Albumin
- Prothrombine (PT)
- INR
- Partial thromboplastin time
- Glucose
- Calcium
- Sodium

- Potassium
- Bicarbonate
- Chloride
- BUN
- Creatinine
- CD3+
- CD4+
- CD8+
- CD45+
- CD16+
- CD56+
- CD19+
- C reactive protein
- Complement C3
- Complement C4
- Complement CH50
- IgG
- IgM
- IgA
- Interleukin-6
- CEA
- AFP
- Ca 15-3
- Ca 19-9

6.9 Child-Pugh score

Child-Pugh score and Child-Pugh category will be calculated according to the following rules:

Child-Pugh Score and Interpretation			
Classification	1	2	3
Serum bilirubin ($\mu\text{mol/L}$)	<34	34-51	>51
Serum albumin (g/L)	>35	28-35	<28
Presence of ascites	Absent	Controllable	Refractory
Encephalopathy	Absent	Minimal	Severe
INR	<1.7	1.7-2.3	>2.3
Interpretation			
Points	Class	Life Expectancy	Perioperative Mortality
5-6	A	15-50 yrs	10%
7-9	B	Candidate for transplant	30%
10-15	C	1-3 months	82%

The categorical variable to be described (n, %) is:

- Child-Pugh category

Descriptive statistics (mean, SD, median, Q_1 , Q_3 , minimum, maximum) of the following continuous variable will be shown:

- Child-Pugh score

6.10 Liver volume reserve

Descriptive statistics (mean, SD, median, Q_1 , Q_3 , minimum, maximum) of the following continuous variable will be shown:

- Liver volume reserve

6.11 Anaesthetic risk assessment

The categorical variable to be described (n, %) is:

- American society of anaesthesiologist score

6.12 Baseline imaging of the target tumor

The categorical variables to be described (n, %) are:

- Technique used for tumor imaging:
 - Magnetic resonance imaging
 - Computed tomography

- Ultrasound with contrast
- Ultrasound without contrast

Descriptive statistics (mean, SD, median, Q₁, Q₃, minimum, maximum) of the following continuous variable will be shown:

- Number of targeted tumors planned to be ablated

The following analyses will be carried out for total targeted tumors (tumor 1 + tumor 2 + tumor 3....):

Descriptive statistics (mean, SD, median, Q₁, Q₃, minimum, maximum) of the following continuous variables will be shown:

- Tumor location: liver segment
- Tumor size:
 - X-axis greatest dimension
 - Y-axis greatest dimension
 - Z-axis greatest dimension
- Volume
- Expected ablation volume

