4 METHODOLOGY

Quantitative variables will be described with measures of central tendency and dispersion: mean, median, SD (standard deviation), Q1 (first quartile) and Q3 (third quartile), minimum and maximum).

Qualitative variables will be described using absolute and relative frequencies (N, %). Two percentage columns will be presented, total percentage (total %) and valid percentage (valid %), that is, the percentage over the sum of valid responses plus missing values and the percentage over the total of valid responses. When there will be not missing values both of them will be equal, and then only one will be shown.

In the analysis of parameters evolution (ablation zone, liver function parameters, immunological parameters, quality of life scores, VAS scale score), among visits, general linear models of repeated measures will be used. With this methodology, it is necessary that the values of the variable must be available at all visits for all patients.

Where an inferential analysis is required, parametric tests shall be used for continuous variables (T-test) that follow a normal distribution. For variables that do not follow a normal (or non parametric) distribution, Mann Whitney (for unpaired data) or Wilcoxon (for paired data) hypothesis tests shall be used.

These tests will be used in all bilateral cases and with a level of significance of 0.05. In cases where a p-value less than 0.05 appears, it refers to the existence of statistical significance.

Due to the number of evaluable patient ablations available, any result from an applied statistical test must be interpreted with caution.

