7.2 Data related to the ablation procedure

The following analyses will be carried out separately for each ablation procedure (ablation 1, ablation 2 and ablation 3):

The categorical variable to be described (n, %) is:

- Has a test pulse energy been applied?

Descriptive statistics (mean, SD, median, Q₁, Q₃, minimum, maximum) of the following continuous variables will be shown:

- Total duration of the procedure (hours, minutes)
- Total duration of the anaesthesia (hours, minutes)

The following analyses will be carried out separately for for total targeted tumors (tumor 1 + tumor 2 + tumor 3....):

The categorical variables to be described (n, %) are:

- Could the ablation be completed?
 - If not, reason will be described

Descriptive statistics (mean, SD, median, Q₁, Q₃, minimum, maximum) of the following continuous variables will be shown:

- Total treatment duration (hours, minutes)
- Treatment mean amplitude

Descriptive statistics (mean, SD, median, Q₁, Q₃, minimum, maximum) of the following continuous variables will be shown:

- Outer contour diameters:
 - X-axis greatest dimension
 - Y-axis greatest dimension
 - Z-axis greatest dimension
- Planned ablation volume
- Diameter D
- Tumor depth ((from skin surface)

The categorical variables to be described (n, %) are:

- Proximity to vital structures, if yes:
 - Near blood vessels
 - Near gallbladder
 - Near Bile ducts
 - Other
- Containing vital structures, if yes:
 - Containing blood vessels
 - Containing gallbladder
 - Other

The following analyses will be carried out separately for each ablation procedure (ablation 1, ablation 2 and ablation 3):

Descriptive statistics (mean, SD, median, Q₁, Q₃, minimum, maximum) of the following continuous variable will be shown:

- Total PAV in case multiple tumors

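### SAP section 6.12 lists the liver segment of the targeted tumours as a continuous variable, against the SAP's own rule in section 4 and its handling in 6.4.2 and 6.5

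*SAP*

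**What the plan says.** Section 6.12 has two kinds of list. The first is categorical and covers the imaging technique. Further down, a block introduced by "The following analyses will be carried out for total targeted tumors" carries a heading that specifies mean, SD, median, quartiles, minimum and maximum "of the following continuous variables will be shown". The first item under that heading is "Tumor location: liver segment". The items after it are the three axis dimensions, the volume and the expected ablation volume, all of them measurements. No n, % line for segment appears anywhere in 6.12.

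Elsewhere the SAP handles the same attribute differently:

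- Section 4 sets the general rule: "Qualitative variables will be described using absolute and relative frequencies (N" and the corresponding percentage).
- Section 6.4.2 (metastases) introduces "Location of tumor nodules: liver segment" with the line "The categorical variable to be described (n, %) is for all records registered". Section 6.5 (hepatocellular carcinoma) does the same.
- For lesions ablated earlier, 6.4.2 again asks for counts and percentages: "Location: liver segment for all records registered (n", %). Section 6.5 does likewise, and 6.4.2 treats resected metastases in the same way.

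**The concern.** A segment number is a name for a region of the liver, not a quantity. Segment 8 is not four times segment 2, and the average of the two is not a place. A mean, SD or quartile of segment labels therefore says nothing reliable about where the tumours lay.

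What is at stake is whether the report shows which segments were treated. A programmer who follows 6.12 literally produces a row that cannot be interpreted or, if segments are stored as text, cannot be computed. A programmer who silently tabulates counts instead departs from the SAP without a record. The targeted tumour is also the unit of the full analysis set and of the technical performance population, so this is the group for which a reader would want the segment table.

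**Working it through.** The SAP gives no figure to reproduce here. The check compares its sections and adds one illustration.

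**Step 1: which summary applies where**

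| SAP section | Lesions covered | Summary of liver segment |
|---|---|---|
| 4 | general rule for qualitative variables | N, % |
| 6.4.2 | all registered nodules, metastases | n, % |
| 6.5 | all registered nodules, hepatocellular carcinoma | n, % |
| 6.4.2 and 6.5 | previously ablated lesions | n, % |
| 6.4.2 | resected metastases | n, % |
| 6.12 | targeted tumours, pooled | mean, SD, median, Q1, Q3, minimum, maximum |

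Only 6.12 departs from the pattern.

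**Step 2: does another section supply the missing table?** Sections 6.4.2 and 6.5 count every registered nodule, in separate tables by tumour type, and do not separate targeted from untreated nodules. Section 7.2 covers the targeted tumours but not their segment. It gives "Tumor depth ((from skin surface"), proximity to vital structures and containment of vital structures. So 6.12 is the only planned summary of segment restricted to the targeted tumours.

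**Step 3: what the literal instruction would produce.** Assume that segments are coded as numbers, and take ten targeted tumours, five in segment 2 and five in segment 8. The coding, the number of tumours and the split are all assumptions; the SAP states none of them.

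- Mean = (5 × 2 + 5 × 8) / 10 = 50 / 10 = 5.0
- Each tumour lies 3 away from the mean, so the sum of squares = 10 × 3² = 90
- SD = √(90 / 9) = √10 = 3.16
- Median = (2 + 8) / 2 = 5

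Mean and median both point to segment 5, where no tumour lies. Summarised under the section 4 rule, the same data read: segment 2, 5 (50%); segment 8, 5 (50%).

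**The case against.** The strongest reply is that this is one item in the wrong list. Section 4 already states the correct rule and 6.4.2 and 6.5 already apply it to this attribute, so a competent programmer has the right treatment in the same document. That is a fair account of how small the risk is, but it does not make 6.12 correct: the specific instruction still contradicts the general one.

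The numerical example can also be criticised. It depends on a coding that the SAP does not give and on a split chosen to make the point. That stands, and the example is an illustration only. The classification error does not depend on it.

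A reader might go further and infer that the SAP has no usable description of where the treated tumours lie. The document does not support this. Section 7.2 plans depth as a continuous variable, and proximity to and containment of vital structures as categorical ones, all for the targeted tumours and with suitable summaries. The all-nodule tables in 6.4.2 and 6.5 should also include the targeted nodules, although they do not identify them.

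A reader might likewise infer that the error weakens the technical success result, or how far it generalises, because location affects acoustic access. The SAP does not link segment to acoustic access or to technical success. Depth is summarised directly in 7.2, and depth and an adequate acoustic window are already eligibility conditions in section 3.2.

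**Conclusion.** Wrong as written, with minor impact. Section 6.12 assigns a nominal variable to continuous summaries, against section 4 and against every other place where the SAP handles liver segment. The consequence is one uninterpretable row in one baseline table, in the only summary of segment specific to the targeted tumours. The primary analysis in section 15.1 does not use segment, so no estimate or denominator there changes.

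The conclusion rests on the SAP text alone. Only the illustrative mean of 5.0 and SD of 3.16 need the assumptions stated with them.

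**What to change.** In section 6.12, take liver segment out of the continuous list and put it under a categorical heading, reported as n and % of targeted tumours. Leave the axis dimensions, volume and expected ablation volume where they are. The cost is one line of the SAP and the matching row of the table shell, with no new data.

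A display of technical success by segment is not part of this correction. With up to ten subjects its cells would probably be very small, and section 4 already asks for caution in interpreting test results because of the small numbers.

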6.13 Quality of life assessment

The score of each dimension of this scale will be calculated according to the established scoring algorithms:

Scoring the EORTC QLQ-C30 version 3.0

	Scale	Number of items	Item range*	Version 3.0 Item numbers	Function scales
Global health status / QoL	QL2	2	6	29, 30	
Global health status/QoL (revised) [†]					
Functional scales					
Physical functioning (revised) [†]	PF2	5	3	1 to 5	F
Role functioning (revised) [†]	RF2	2	3	6, 7	F
Emotional functioning	EF	4	3	21 to 24	F
Cognitive functioning	CF	2	3	20, 25	F
Social functioning	SF	2	3	26, 27	F
Symptom scales / items					
Fatigue	FA	3	3	10, 12, 18	
Nausea and vomiting	NV	2	3	14, 15	
Pain	PA	2	3	9, 19	
Dyspnoea	DY	1	3	8	
Insomnia	SL	1	3	11	
Appetite loss	AP	1	3	13	
Constipation	CO	1	3	16	
Diarrhoea	DI	1	3	17	
Financial difficulties	FI	1	3	28	

* *Item range* is the difference between the possible maximum and the minimum response to individual items; most items take values from 1 to 4, giving *range* = 3.

† (revised) scales are those that have been changed since version 1.0, and their short names are indicated in this manual by a suffix “2” – for example, PF2.

For all scales, the *RawScore*, *RS*, is the mean of the component items:

$$RawScore = RS = (I1 + I2 + \dots + In) / n$$

Then for **Functional scales**:

$$\square \quad Score = [1 - ((RS-1)/range)] * 100$$

and for **Symptom scales / items** and **Global health status / QoL**:

$$Score = \{(RS - 1) / range\} * 100$$

Examples:

Emotional functioning:

$$RawScore = (Q_{21} + Q_{22} + Q_{23} + Q_{24}) / 4$$

$$EF\ Score = \{1 - (RawScore - 1) / 3\} \times 100$$

Fatigue:

$$RawScore = (Q_{10} + Q_{12} + Q_{18}) / 3$$

$$FA\ Score = \{(RawScore - 1) / 3\} \times 100$$

Missing items:**• Have at least half of the items from the scale been answered?**

- If Yes, use all the items that were completed, and apply the standard equations given on the previous pages for calculating the scale scores; ignore any items with missing values when making the calculations.
- If No, set scale score to missing.
- For single-item measures, set score to missing.

Descriptive statistics (mean, SD, median, Q₁, Q₃, minimum, maximum) of the following continuous variables will be shown:

- Global health status/QoL (revised)
- Physical functioning (revised)
- Role functioning (revised)
- Emotional functioning
- Cognitive functioning
- Social functioning
- Fatigue
- Nausea and vomiting
- Pain
- Dyspnoea
- Insomnia
- Appetite loss
- Constipation
- Diarrhoea
- Financial difficulties

7 DESCRIPTIVE ANALYSIS: VISIT 1: ABLATION PROCEDURE

The categorical variables to be described (n, %) are:

- Number of ablations procedures
- Number or targeted tumors per ablation procedure
- Number of re-treatments

7.1 Pain assessment

The following analyses will be carried out separately for each ablation procedure (ablation 1, ablation 2 and ablation 3):

Descriptive statistics (mean, SD, median, Q₁, Q₃, minimum, maximum) of the following continuous variable will be shown:

- VAS score

7.2 Data related to the ablation procedure

The following analyses will be carried out separately for each ablation procedure (ablation 1, ablation 2 and ablation 3):

The categorical variable to be described (n, %) is:

- Has a test pulse energy been applied?

Descriptive statistics (mean, SD, median, Q₁, Q₃, minimum, maximum) of the following continuous variables will be shown:

- Total duration of the procedure (hours, minutes)
- Total duration of the anaesthesia (hours, minutes)

The following analyses will be carried out separately for for total targeted tumors (tumor 1 + tumor 2 + tumor 3....):

The categorical variables to be described (n, %) are:

- Could the ablation be completed?
 - If not, reason will be described

Descriptive statistics (mean, SD, median, Q₁, Q₃, minimum, maximum) of the following continuous variables will be shown:

- Total treatment duration (hours, minutes)
- Treatment mean amplitude

Descriptive statistics (mean, SD, median, Q₁, Q₃, minimum, maximum) of the following continuous variables will be shown:

- Outer contour diameters:
 - X-axis greatest dimension
 - Y-axis greatest dimension
 - Z-axis greatest dimension
- Planned ablation volume
- Diameter D
- Tumor depth ((from skin surface)

The categorical variables to be described (n, %) are:

- Proximity to vital structures, if yes:
 - Near blood vessels
 - Near gallbladder
 - Near Bile ducts
 - Other
- Containing vital structures, if yes:
 - Containing blood vessels
 - Containing gallbladder
 - Other

The following analyses will be carried out separately for each ablation procedure (ablation 1, ablation 2 and ablation 3):

Descriptive statistics (mean, SD, median, Q₁, Q₃, minimum, maximum) of the following continuous variable will be shown:

- Total PAV in case multiple tumors

